#### Power Statement:

Assuming a response rate of 50% (i.e. 150 treatment responders and 150 treatment non-responders), and assuming that 1000 independent SNPs will be evaluated and thus a significance level of  $5*10^{-5}$  will be used for analysis, this study will have 80% power to detect odds ratios of 2.90 for SNPs with minor allele frequency of 0.2, or odds ratios of 2.35 for SNPs with minor allele frequency of 2.35.

However, there is a lack of consistency in results from prior studies of association of different genotypes (and GWA studies) in depression response to medication. There are two critical factors that influence the result of pharmacogenomics and genetic-translational studies in general; 1. The number of recruited participants, and 2. A well characterized phenotype (Hennekam and Biesecker 2012). Recent meta-analysis on pharmacogenomics of antidepressants have identified the necessity for more homogeneous phenotypes needed for stronger associations (GENDEP, MARS and STAR\*D Investigators, 2013). Using publically available data from the GAIN consortium, our group has demonstrated that the number of participants needed to find genetic associations in complex phenotypes, when they are homogeneous, can be reduced considerably (unpublished data; Winham, 2013). This study will focus on a strict homogeneous and highly reliable phenotypic classification of participants, both for treatment response and adverse events. In addition, unlike rigorous traditional clinical trials, pharmacogenomics trials benefit from a more "real practice setting" in the sense of including participants with comorbidity and non-ideal treatment panoramas like ours (Mrazek and Lerman, 2011).

We propose to use a pharmacogenomic approach to study the contribution of genetic variation in fluoxetine pharmacokinetic and pharmacodynamic pathways to variation in drug response to lamotrigine and fluoxetine in bipolar depression. The genes in each of the pathways to be studied will be tested, not merely for individual SNPs, but rather by selecting htSNPs for intragene haplotypes for genes that encode proteins which participate in these pathways.

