### **AIMS:**

1. To evaluate the association between genotype and haplotype variations in candidate genes involved in pharmacodynamic and pharmacokinetic pathways of treatment response to lamotrigine (n=200) or fluoxetine (n=200) in bipolar depression. In addition, we aim to perform exploratory analyses of single-nucleotide polymorphisms (SNPs) obtained from GWA studies with drug response phenotypes.
2. To evaluate the association between genotype and haplotype variations in candidate genes involved in pharmacodynamic and pharmacokinetic pathways of drug adverse events to treatment [rash emergence and antidepressant induced mania (AIM+) to lamotrigine (n=200) or fluoxetine (n=200) respectively in bipolar depression. In addition, we aim to perform exploratory analyses of single-nucleotide polymorphisms (SNPs) obtained from GWA studies with drug adverse events phenotypes.

3. To identify blood and brain metabolites associated with treatment response to lamotrigine (n=200) and fluoxetine (n=200) in bipolar depression.

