### **Hypothesis:**

1. Treatment response to lamotrigine (n=200) or fluoxetine (n=200) in comparison to non-response, will be associated with different allele variation (either at a genotypic, haplotype or interaction level) in pharmacodynamic/pharmacokinetic functionally related genes.
2. Development of adverse event (rash or AIM+) while undergoing treatment with, lamotrigine (n=200) or fluoxetine (n=200) in comparison to no adverse event, will be associated with different allele variation (either at a genotypic, haplotype or interaction level) in pharmacodynamic/pharmacokinetic functionally related genes.
3. Treatment response to lamotrigine (n=200) or fluoxetine (n=200) in comparison to non-response, will be associated with biomarker expression (epigenetic and metabolomic/proteomic) in functionally related biological systems.

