### **Participant Population:**

Number of participants (total, each subgroup including anticipated dropouts, screen failures, nonvisible scan data) 1000 total, n=200 lamotrigine participants, n=200 fluoxetine participants.

Site	Anticipated Sample Collection
Mayo Clinic (Rochester and Austin)	400
Lindner Center of HOPE	100

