### Data Analysis:

We will investigate association between the primary endpoints a set of SNPs in the gene candidates and/or GWA studies to evaluate a greater number of SNPs and bioinformatics tools to perform pathway analysis. Primary analyses will evaluate the association between treatment response and adverse events phenotypes and SNPs in candidate genes by comparing genotype frequencies between the treatment responder and non-responder groups and the presence/absence of adverse events, using logistic regression, assuming a log-additive model for

allele effects. Logistic regression will enable multivariate analyses, and in particular to assess genetic effects on treatment response and adverse events, while adjusting for other possible risk factors, and modeling gene-environment interactions. Covariates modeled in the analysis will include age of onset of bipolar disorder, and presence or absence of circadian rhythm liability, concomitant medication, alcohol abuse or dependence comorbidity (lifetime), stressful events (defined as presence or absence of any stressful event in the last 12 months and as a score that will summarize the number of stressful events in the prior 12 months), binge eating, body mass index measures and other relevant phenotypes.

A large majority of the Mayo Clinic Rochester participant population is white, non-Hispanic. However, due to the greater ethnic diversity of participants at the other sites, we anticipate that approximately 25% of our sample may come from other racial or ethnic groups. Therefore, all of our genetic analyses will be adjusted for self-reported ethnicity and secondary analyses will be undertaken within ethnically homogeneous subgroups.

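### The 80% power is calculated for 300 patients, a number the plan never derives; for the per-drug question in Aim 1 (200 per drug) it is about 48%, and the second allele frequency, 2.35, is impossible

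*Combined protocol and SAP*

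**What the plan says.** All references are to the combined protocol and SAP.

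- **Power Statement.** The calculation starts from "Assuming a response rate of 50% (i.e. 150 treatment responders and 150 treatment non-responders". It assumes that "1000 independent SNPs will be evaluated and thus a significance level of" 5×10⁻⁵ applies, and claims 80% power for an odds ratio of 2.90 at minor allele frequency (MAF) 0.2. The second scenario reads "odds ratios of 2.35 for SNPs with minor allele frequency of 2.35".
- **Aims, Aim 1.** The target is candidate-gene variation in "pathways of treatment response to lamotrigine (n=200) or fluoxetine (n=200) in bipolar depression".
- **Hypothesis 1.** "Treatment response to lamotrigine (n=200) or fluoxetine (n=200) in comparison to non-response" is to be associated with allele variation.
- **Data Analysis.** The primary analysis is a log-additive logistic regression, "comparing genotype frequencies between the treatment responder and non-responder groups". The section does not say whether models are fitted per drug or on both drugs together, and its named covariates do not include randomised drug. It also expects that "approximately 25% of our sample may come from other racial or ethnic groups", handled by adjustment for self-reported ethnicity, with analyses inside ethnic groups as secondary.
- **Participant Population.** The counts are 1000 in total and 200 per drug, under a heading that describes them as "each subgroup including anticipated dropouts, screen failures, nonvisible scan data". The site table adds to 400 + 100 = 500. No dropout rate is given.

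**The concern.** At the plan's own 50% response rate, 200 patients on one drug give 100 responders and 100 non-responders, so 150 against 150 cannot describe either drug. Nor does 300 match any count in the documents: 200 per drug, 400 randomised, 500 in the site table, 1000 in total. It equals 75% of 400, but the Power Statement does not say that dropout or ethnicity was the reason.

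A reader would take the 80% as support for the drug-specific hypotheses. If it belongs to a different population, the plan gives no power figure for its leading question, and a null result within one drug could be over-read. The second scenario cannot be checked at all as printed, because a minor allele frequency cannot exceed 0.5.

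**Working it through.** **Inputs.** Response rate 50%, odds ratios 2.90 and 2.35, first MAF 0.2, and significance level 0.05/1000 = 5×10⁻⁵ (Power Statement); log-additive logistic model (Data Analysis); 200 per drug (Aim 1, Hypothesis 1). Assumptions of mine: two-sided test, Hardy-Weinberg genotype proportions, MAF defined in the whole sample, and MAF 0.4 for the second scenario.

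**Method.** Likelihood-ratio test on 1 degree of freedom.

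- Genotype frequencies for x = 0, 1, 2 minor alleles: g = (1−q)², 2q(1−q), q².
- Response probability: logit p(x) = a + x·ln(OR), with a chosen so that Σ g·p = 0.5.
- Non-centrality per patient: λ = 2{Σ g[p ln p + (1−p) ln(1−p)] − ln 0.5}.
- Power = P(χ²₁ with non-centrality Nλ exceeds 16.448), where 16.448 is the critical value at 5×10⁻⁵. Power of 80% needs Nλ = 23.98.

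**Numbers put in.**

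- OR 2.90, MAF 0.2: g = 0.64, 0.32, 0.04; a = −0.409; p = 0.399, 0.658, 0.848; λ = 0.08023.
- OR 2.35, MAF 0.4: g = 0.36, 0.48, 0.16; a = −0.679; p = 0.336, 0.544, 0.737; λ = 0.08029.

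| Patients analysed | Nλ (2.90 / 2.35) | Power, OR 2.90, MAF 0.2 | Power, OR 2.35, MAF 0.4 |
|---|---|---|---|
| 300 (plan) | 24.07 / 24.09 | 80.2% | 80.3% |
| 200 (one drug, all evaluable) | 16.05 / 16.06 | 48.0% | 48.1% |
| 150 (one drug, assumed 25% loss) | 12.04 / 12.04 | 27.9% | 27.9% |
| 400 (both drugs pooled, shared effect) | 32.09 / 32.12 | 94.6% | 94.7% |

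The first row reproduces the plan's 80%. It also shows why 0.4 is the likely second MAF: at N = 300 and OR 2.35, 80% power is reached at MAF about 0.39. Simulation with 20,000 replicates gave 81.6% and 81.6% at 300, and 48.8% and 49.1% at 200.

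**Sample size needed.** 23.98/0.08023 = 298.9 and 23.98/0.08029 = 298.7, so 299 evaluable patients per drug in either scenario.

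**Odds ratio detectable with 80% power.**

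| Patients analysed | MAF 0.2 | MAF 0.4 |
|---|---|---|
| 300 | 2.89 | 2.35 |
| 200 | 3.82 | 2.91 |
| 150 | 4.92 | 3.54 |

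**Sensitivity at 200 per drug.**

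- Unknown second MAF: for OR 2.35, power is 38% at MAF 0.3 and 51% at 0.5.
- Response rate 40% or 60% instead of 50%: 51% or 39% (OR 2.90); 46% or 43% (OR 2.35).
- MAF defined in non-responders: 75% and 55% two-sided, 80% and 61% one-sided. That definition does not reproduce the plan's figure at 300 (95.9% and 85.6% two-sided). For OR 2.35, no MAF up to 0.5 under either definition exceeds 55% two-sided or 61% one-sided. No reading gives 80% in both scenarios.

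**Pooled reading.** With a drug term and one common SNP effect, power at OR 2.90 and MAF 0.2 depends on the effect in the other drug:

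| OR in the other drug | N = 300 | N = 400 |
|---|---|---|
| 2.90 (shared) | 80% | 95% |
| 2.0 | 52% | 75% |
| 1.5 | 26% | 46% |
| 1.0 (none) | 5% | 10% |

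**The case against.** The strongest reply is that the sponsor meant a pooled analysis. The Data Analysis section compares responders with non-responders without splitting by drug, and the Power Statement speaks of response to both drugs. On that reading the arithmetic is right at 300 and conservative at 400. This stands as far as it goes: the calculation itself is sound, and the 48% is conditional on per-drug models. It does not settle the matter, because the aims and hypotheses name each drug with its own 200 patients, and a pooled model supports 80% only for a shared effect.

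The 5% and 10% figures for an effect in one drug only are a worst case. A joint 2-degree-of-freedom test of SNP and SNP-by-drug terms raises them to about 20% at 300 and 37% at 400, still far below 80%.

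Three smaller points also stand. The 150 per drug is an illustration, since the plan gives no dropout rate. The exact figures depend on the test: at 300 and OR 2.90, a Wald approximation gives 72% and a score test 78%. The 2.35 is plainly a slip. It still leaves one of two scenarios unusable until the sponsor confirms the intended value.

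**Conclusion.** The concern holds. The 80% is correct for 300 patients, but 300 is underived and cannot be one drug's sample. For the drug-specific question, power at the stated odds ratios is about 48%, assuming per-drug models, all 200 patients evaluable, 50% response, a two-sided 5×10⁻⁵ level and, for the second scenario, MAF 0.4. Because the Participant Population heading says its counts include dropouts, 200 may be an upper limit, and 48% would then be optimistic. The printed MAF of 2.35 is impossible on any reading. The fault lies in the mismatch between the power population and the aims, plus one misprint. The power paragraph needs correction because it is the plan's only power calculation.

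**What to change.** 1. In Data Analysis, state whether the primary models are fitted per drug or pooled. In the Power Statement, give the number of evaluable patients and how it was derived.
2. If per drug, restate the calculation: 200 patients per drug, 100 responders and 100 non-responders at 50% response, two-sided level 5×10⁻⁵, 80% power for an odds ratio of about 3.8 at MAF 0.2 and about 2.9 at MAF 0.4. Add a line for the expected evaluable number; if that were 150 per drug, the odds ratios would be about 4.9 and 3.5.
3. If 300 was a pooled evaluable sample, show its derivation, specify the model with drug and SNP-by-drug terms, and say that the 80% applies to a shared effect and not to the drug-specific hypotheses.
4. Correct the MAF of 2.35. The value 0.4 fits the stated odds ratio at 300, but the sponsor should confirm it.

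The cost is one rewritten paragraph and one added sentence. The detectable effects become less favourable under the per-drug reading. No extra patients are needed.

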#### **Human Safety Aspects Risks: PROTECTION OF HUMAN PARTICIPANTS**

##### **1. Risks to the Participants**

1a. Human Participants Involvement & Characteristics: The project will involve individuals with a DSM-IV diagnosis of bipolar disorder type I or II depressive episode. All participants will be aged 18-65 years and will be in relatively good physical health with no unstable medical conditions.

1b. Sources of Materials: Psychiatric diagnoses, psychiatric history, and other data collected from study participants will be obtained using standardized interviews and self-report measures. In addition, medical records may be obtained. This will be obtained specifically for research purposes. For laboratory analyses, samples of blood and urine will be obtained from participants for research purposes.

1c. Potential Risks: The risk of participating in a clinical interview is no greater than routine clinical care (i.e., minimal risk). Participating in mood interviews. The material covered is routine and consists of questions that they would be asked by the psychiatrists under normal clinical conditions. Standardized instruments will be administered. Participants are asked to answer questions on a voluntary basis and are told that uncomfortable questions do not have to be answered. Some questions that will be asked during the study interviews or questionnaires may make study participants uncomfortable. Participants have the right to choose not to answer any questions that are uncomfortable to them.

The risks of having blood drawn include pain, bruising, or, rarely, infections at the site of needle stick. These risks are no different than with any routine clinical blood draw.

There is the possibility that a participant's personal information could accidentally be disclosed. It is possible that this information could potentially be used to discriminate against a person, including socially or for insurance or employment purposes. The Bipolar Biobank will utilize safeguards such as de identifying data, using secure servers for databases, using locked storage for any hard-copy information, and privacy training to help ensure that a participant's information is not disclosed.

Researchers may determine that certain research findings may be valuable to participants. The risks to participants of learning the results of genetic testing can include emotional upset, changes in relationships, and/or insurance or employment discrimination. The Bipolar Biobank Managing Group and Phenotypic Concordance Committee will work with the Mayo Clinic Biospecimen Trust Oversight Group (BTOG) to determine if test results should be offered to participants. If results are offered, participants will have the option to decline learning the information. If results are offered, it may be necessary for the participant to meet with a health care professional, such as a psychiatrist or genetic counselor.

#### Possible Risks for study medications

Fluoxetine is FDA approved for unipolar depression in adult and pediatric populations. Double-blind, randomized controlled studies in monotherapy (Cohn et al., 1989) and as a combination with olanzapine (Tohen et al., 2003; Brown et al., 2006) have found it effective for the treatment of bipolar depression. All participants will be informed of all known side effects. The most commonly observed side effects of fluoxetine are lightheadedness, fainting, dizziness, confusion, hallucinations, rhinitis, dry mouth, tremor, nausea, ejaculation disorder (primarily ejaculatory delay), impotence, fatigue, diarrhea, sleep disorders (somnolence), and sweating. The FDA has issued a black box warning for fluoxetine regarding antidepressants increased the risk compared to placebo of suicidal thinking and behavior (suicidality) in children, adolescents, and young adults in short-term studies of major depressive disorder and other psychiatric disorders.

For bipolar depressed participants participating in the open lamotrigine trial, lamotrigine is FDA approved for the maintenance phase of bipolar disorder. Although we are using the FDA bipolar drug in a different phase than its original indication, there is placebo-controlled data showing efficacy in the phase that we are studying (Calabrese et al., 1999; Frye, M.A. et al., 2000).

Most side effects of lamotrigine are mild and go away without stopping the drug. The most frequent side effects include dizziness, muscular incoordination, drowsiness, headache, insomnia, double-vision, blurred vision, bradycardia (slow heart rate), nausea, vomiting. If any of these side effects are experienced, the subject must not drive a motor vehicle until these symptoms have stopped.

Approximately 16% of participants receiving lamotrigine for Bipolar Disorder in premarketing trials discontinued therapy because of an adverse experience – most commonly due to rash (5%) and mania/hypomania/mixed mood adverse events (2%).

Based on older guidelines for dosing of lamotrigine, there were some serious side effects, which in clinical trials of bipolar and other mood disorders occurred in approximately 0.08% (0.8 per 1,000) of adults taking lamotrigine as initial monotherapy and 0.13% (1.3 per 1,000) in adults receiving lamotrigine as adjunctive therapy. These side effects can be serious and potentially life-threatening. These are mainly side effects related to the skin, and include Stevens Johnson Syndrome (a severe rash around the eyes, mouth, genital, anal, and other skin areas), toxic epidermal necrolysis (severed blistering and sloughing of the skin), angioedema (swelling under the skin), and hypersensitivity syndrome (an allergy-like reaction with fever, swollen glands, rash, blood or liver problems, and facial swelling). Almost all of the life-threatening rashes have occurred within 2 to 8 weeks after starting to take lamotrigine. However, there have been a few people who developed these rashes months after starting lamotrigine. The only known factor that has been identified to predict the risk of the occurrence or severity of lamotrigine associated rash is age; pediatric participants are at greater risk than adults. Three factors have been suggested as potential causes for an increased risk of serious rash: 1) starting at too high of a dose, 2) increasing the dose too quickly, and 3) coadministration with valproate. The risk is increased to 1 out of every 100 adults who take a combination of lamotrigine and divalproex sodium. In worldwide post-marketing experience, rare cases of rash-related death have been reported, although the numbers are too few to estimate a risk. However, these deaths occurred when using the old dose recommendations. New data would suggest that with more conservative guidelines, as noted in the Physician's Desk Reference and as being followed in this study, this risk is reduced.

Non-serious rashes also occur when taking lamotrigine; however, it is not possible to know which rashes will become severe. Thus any rash, skin discoloration, blister, or mouth sore should be reported immediately. In general, lamotrigine should be discontinued at the first sign of rash, unless the rash is clearly not drug-related. Even if one stops taking lamotrigine, a rash could become severe or permanently disabling or disfiguring. In extremely rare cases, multiorgan failure has been observed in 2

out of 3,796 participants. In clinical trials with bipolar disorder participants, 2 participants experienced seizures shortly after abrupt withdrawal of lamotrigine. Though there were confounding factors that may have contributed to the occurrence of those seizures, it is important that lamotrigine should not be abruptly discontinued. Unless safety concerns warrant otherwise, the dose of lamotrigine should be tapered over at least a period of 2 weeks. Overdoses of up to 15 g have been reported, some of which were fatal. Overdose can result in ataxia, nystagmus, increased seizures, decreased consciousness level, coma, and intraventricular conduction delay. A recent findings based on FDA's review of adverse event reports submitted to the agency from December 1994 (when the drug was approved) through November 2009 indicate that Lamictal may pose a rare but increased risk associated with aseptic meningitis. A total of 40 cases of aseptic meningitis occurring in pediatric and adult participants taking lamotrigine were identified. The symptoms present in these cases included headache, fever, nausea, vomiting, nuchal rigidity, rash, photophobia and myalgias. These symptoms occurred 1 to 42 days after starting Lamictal. There was one reported death, although the death was not thought to be the result of aseptic meningitis. In most cases, symptoms resolved after lamotrigine was discontinued. Fifteen of these cases reported a rapid return of symptoms following re-initiation of Lamictal; symptoms recurred within 30 minutes to 24 hours following re-initiation of lamotrigine. Symptoms were frequently more severe after re-exposure. Although this is currently not a black box warning, this new rare but serious side effect will be included on an updated black box warning insert for lamotrigine. The research data for this study will be shared as part of the NIH Data Share policy. All participants will be identified by a unique enrollment identification number that will maintain their anonymity. All shared data will be coded by this I.D. All personal information will be kept separate and locked in a file only accessible by the Principal Investigators.

The above research pose greater than minimal risk to the subject, but are reasonable in relation to the anticipated benefits to better understanding of the illness. There is no guarantee that the study medication will improve a participant's condition. Based on prior research, we anticipate that those taking lamotrigine will experience improvements. Overall participation will provide useful scientific information about the study medication and its benefits for future participants with bipolar disorder complicated by alcohol abuse or dependence. Alternative treatments are available for bipolar depression and include the following medications: Lithium, divalproex sodium (Depakote®) carbamazepine (Tegretol®), atypical antipsychotics, and antidepressants. Electroconvulsive therapy is a non-medication alternative mood treatment.

**Protection Against Risk:** Participants will be assured that they do not need to answer any question on the mood or functional scales that which they do not wish to address. Participants will be fully informed of the risks of the medication and strongly advised to notify the doctor immediately if any symptoms of serious side effects (rash, aseptic meningitis or other hypersensitivities, antidepressant induced mania, serotoninergic syndrome) are noticed. The physician will discuss the symptoms with the participant. These symptoms are also detailed in the informed consent form. Subject will be cautioned to keep medication out of reach of children or others of limited capacity to read or understand because it may cause serious side effects and possible death. Participants will be carefully monitored throughout the study for either intolerable mood effects or medication side effects, and the doctor will discontinue a subject from the study if his/her psychiatric condition worsens, and will follow-up closely with other recommendations for treatment.

During the course of treatment with lamotrigine, participants will be closely monitored for any serious adverse cutaneous reactions (as mentioned above in drop-out section), rashes, aseptic meningitis, or hypersensitivities. Fluoxetine participants will be monitored closely for AIM+ or appearance of suicidal ideation/planning. If a subject notices any such symptoms, he/she will immediately report to the study doctor.

If the subject is a woman able to become pregnant, she will not participate in this research study unless she has a negative urine pregnancy test, is not breast-feeding, and is using an approved method of birth control. The following are considered to be approved methods of birth control: 1) intrauterine device (IUD), 2) barrier protection, 3) a contraceptive implantation system (Norplant), 4) oral contraceptive pills, 5) a surgically sterile partner, or 6) abstinence. Female participants will be instructed to inform the principal investigator if they have any reason to suspect pregnancy, if their circumstances have changed and there is now a risk of becoming pregnant, or they have stopped using an approved form of birth control. If a subject becomes pregnant, intends to start breast-feeding, or starts to breast-feed, she must notify the study doctor, because the effects of study medication on unborn or nursing

children are unknown. In the case of pregnancy, the study doctor can contact the Lamotrigine Pregnancy Registry for information by calling [name]. Male subject will be required to use birth control methods.

